7.6 Safety Analysis

7.6.1 Adverse Events

All AEs will be coded by system organ class and Medical Dictionary for Regulatory Activities (MedDRA) preferred term.

7.6.1.1 Open-label Stabilization Phase

The incidence of the following events during the open-label stabilization phase will be summarized for the Open-label Safety Sample:

- TEAEs
- TEAEs by severity
- TEAEs potentially causally related to the IMP
- TEAEs with an outcome of death
- Serious TEAEs
- TEAEs leading to discontinuation of the IMP

7.6.1.2 Double-blind Randomized Withdrawal Phase

The incidence of the following events during randomized withdrawal phase will be summarized for the Randomized Safety Sample:

- TEAEs
- TEAEs by severity
- TEAEs potentially causally related to the IMP
- TEAEs with an outcome of death
- Serious TEAEs
- TEAEs leading to discontinuation of the IMP

The above summaries will also be prepared for TEAEs potentially causally related to the IMP.

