Subjects entering the double-blind randomized withdrawal phase will be randomized 1:1:1 to the half-dose arm, full-dose arm, or placebo arm. Doses in the aripiprazole arms will be based on the subject's stabilized dose during the single-blind stabilization phase. Subjects will be monitored for relapse during the double-blind randomized withdrawal phase. Relapse is defined as a loss of $\geq 50\%$ of the improvement experienced during the open-label stabilization phase (ie, improvement at the last assessment of YGTSS before randomization) on the YGTSS TTS. If a subject meets relapse criteria, they should be discontinued and treated according to the schedule of assessments.

There will also be a safety follow-up period (30 + 3 days) after the last dose of IMP or after the clinical site is notified that the subject prematurely discontinued their IMP.

During the pretreatment phase, modifications to a subject's pre-existing treatment are not to be made for the explicit purpose of entering this trial, but should be done only where deemed clinically appropriate by the investigator. Tapering rates for washout of medications are at the discretion of the investigator and are to be determined on an

Protocol 31-14-204

individual basis, with consideration to the subject's clinical condition, dose, and known pharmacokinetics (PK) of the medication being tapered, as long as the protocol-mandated discontinuation timeframe is met. The exception is a long-acting depot medication, which cannot be tapered and would be discontinued after the informed consent/assent is obtained.

[figure not shown]

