3.2.2 Double-blind Randomized Withdrawal Phase

Subjects meeting the stabilization criteria will be randomized in a 1:1:1 ratio to the half-dose arm, full-dose arm, or placebo arm based on their stabilized dose in the open-label stabilization phase. Weight-based dosing will be determined using the body weight measurement from the open-label stabilization phase baseline. See [Table 3.2.2-1](#) for the dosing schedule.

All subjects will take 2 tablets once daily. The 20.0 mg/day dose taken as two 10-mg tablets. No dose adjustments will be allowed in the double-blind randomized withdrawal phase.

Weight Group	Stabilized Dose	Double-blind Randomized Withdrawal Phase Doses		
		Full-dose Arm	Half-dose Arm	Placebo Arm
< 50kg	5 mg	5 mg	2 mg	Matching placebo
	10 mg	10 mg	5 mg	Matching placebo
≥ 50 kg	10 mg	10 mg	5 mg	Matching placebo
	20 mg	20 mg	10 mg	Matching placebo

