7.1 Sample Size

The planned sample size for the double-blind randomized withdrawal phase is 114 subjects (ie, 38 subjects per treatment group). Assuming the proportion of randomized subjects experiencing relapse during the double-blind randomized withdrawal phase will be 65% in the placebo group and 34% in each of the 2 aripiprazole dose groups, 114 subjects will provide approximately 80% power to detect a hazard ratio of 0.4 for relapse (either aripiprazole dose group versus placebo) at the alpha level of 0.05 (2-sided). Under the above assumptions, a total of 51 relapse events are expected to be observed during the randomization phase. However, subject enrollment will stop when 51 relapse events have accrued or 114 subjects have been randomized, whichever occurs earlier.

The sample size will allow one IA at approximately 70% of events accrual time point. The O'Brien-Fleming boundaries were used for sample size calculation of the interim analysis so that the interim analysis will be conducted when 36 relapse events occur.¹⁹ The 2-sided alpha levels for the IA is 0.016, and the alpha left for the final analysis will be 0.045.

In order to randomize 114 subjects, approximately 228 subjects will need to enter the open-label stabilization phase of the trial, assuming that the stabilization rate is 50%.

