7.1 Subject Disposition

Disposition of subjects including screened subjects and/or randomized subjects will be reported by phase and treatment group. Subject enrollment will be summarized by age group (6-12 years old and 13-17 years old), region, country and center. Durations of subjects staying in each phase will be summarized by treatment group. Reasons for discontinuations will be tabulated by phase and treatment group. Subjects who complete the Week 12 visit of the double-blind randomized withdrawal phase are defined as trial completers.

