9.1 Extent of Exposure

Exposure to IMP for randomized safety sample in open-label stabilization phase and double-blinded randomized withdrawal phase will be summarized in percentage of subjects' exposure and average daily dose for each week by treatment group in randomized phase. Exposure to IMP for open-label safety sample during open-label stabilization phase will be also provided in percentage of subjects' exposure and average daily dose by week.

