9.2 Adverse Events

All adverse events (AEs) are coded by system organ class and Medical Dictionary for Regulatory Activities (MedDRA) preferred term (Version 23.0 or later). A treatment-emergent AE (TEAE) is defined as an AE which starts after start of trial medication (Aripiprazole IM depot/Oral tablets), or an AE continues from baseline of the specific phase and becomes serious, trial drug-related or results in death, discontinuation, interruption or reduction of study medication during this phase. The incidences of the following treatment-emergent adverse events (TEAEs) will be summarized by treatment group for the safety samples:

- TEAEs by severity
- Potentially drug related TEAEs
- TEAEs with an outcome of death
- Serious TEAEs
- Discontinuations due to TEAEs
- Death
- Non- Serious TEAEs

Deaths, SAEs, and AEs leading to discontinuation from the trial will be listed for the safety samples.

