- CT-5.5.2 Clinical Global Impressions Scale for Tourette's Syndrome (CGI-TS) Improvement Score - Mean by Week - OC (ITT Sample)
- CT-6.1.1 Simpson-Angus Scale Total Score - Mean Change from Baseline by Week - OC (Randomized Safety Sample)
- CT-6.1.2 Barnes Akathisia Rating Scale Global Score - Mean Change from Baseline by Week - OC (Randomized Safety Sample)
- CT-6.1.3 AIMS Movement Rating Score - Mean Change from Baseline by Week - OC (Randomized Safety Sample)
- CT-6.2.1 Columbia-Suicide Severity Rating Scale (C-SSRS) (children's version) - Suicidality (Randomized Safety Sample)
- CT-6.2.2 Columbia-Suicide Severity Rating Scale (C-SSRS) (children's version) by Type (Randomized Safety Sample)
- CT-7 Extent of Exposure to Investigational Medicinal Products Double-Blind Randomized Withdrawal Phase (Randomized Safety Sample)
- CT-8.1 Adverse Events (All Causalities) (Randomized Safety Sample)

- CT-8.2.1 Incidence of Treatment-Emergent Adverse Events by System Organ Class and MedDRA Preferred Term (Randomized Safety Sample)
- CT-8.2.2 Incidence of Treatment-Emergent Adverse Events by System Organ Class, MedDRA Preferred Term and Severity (Randomized Safety Sample)
- CT-8.2.3 Incidence and Occurrence (Number of Events) of non-Serious Treatment-emergent Adverse by System Organ Class and MedDRA Preferred Term (Randomized Safety Sample)
- CT-8.3.1 Incidence and Occurrence (Number of Events) of Potentially Drug-Related Treatment-Emergent Adverse Events by System Organ Class and MedDRA Preferred (Randomized Safety Sample)
- CT-8.3.2 Incidence of Potentially Drug-related Treatment-emergent Adverse Events by System Organ Class and MedDRA Preferred Term and Severity (Randomized Safety Sample)
- CT-8.4 Incidence of Deaths Due to Treatment-Emergent Adverse Events by System Organ Class and MedDRA Preferred Term (Randomized Safety Sample)
- CT-8.5.1 Incidence and Occurrence (Number of Events) of Serious Treatment-Emergent Adverse Events by System Organ Class and MedDRA Preferred Term (Randomized Safety Sample)
- CT-8.5.2 Incidence of Serious Treatment-emergent Adverse Events by System Organ Class and MedDRA Preferred Term and Severity (Randomized Safety Sample)
- CT-8.6.1 Incidence of Treatment-Emergent Adverse Events Resulting in Discontinuation from Trial by System Organ Class and MedDRA Preferred Term (Randomized Safety Sample)

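### The double-blind adverse event tables have no time-at-risk denominator, although relapse ends participation and the plan expects relapse to be more frequent on placebo

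*Protocol*

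**What the plan says.** - **Adverse event measure.** Protocol Section 7.6.1.2 states: "The incidence of the following events during randomized withdrawal phase will be summarized for the Randomized Safety Sample". SAP Section 9.2 adds the arm: "The incidences of the following treatment-emergent adverse events (TEAEs) will be summarized by treatment group for the safety samples".
- **Tables.** SAP Appendix 4 lists CT-8.1 to CT-8.6.2 for the Randomized Safety Sample. CT-8.2.3 (non-serious), CT-8.3.1 (potentially drug-related) and CT-8.5.1 (serious) also give the number of events. Neither document mentions a rate per unit of exposure, a person-time denominator, a time-to-first-event summary or an onset-interval table for adverse events.
- **What ends observation.** Protocol Section 3.1: "If a subject meets relapse criteria, they should be discontinued and treated according to the schedule of assessments".
- **Expected relapse.** Protocol Section 7.1 assumes "65% in the placebo group and 34% in each of the 2 aripiprazole dose groups".
- **Exposure is reported, but elsewhere.** SAP Section 7.1: "Durations of subjects staying in each phase will be summarized by treatment group". SAP Section 9.1 summarises exposure and "average daily dose for each week by treatment group in randomized phase".
- **Status.** SAP Sections 8.1.1 and 14 state that the trial ended early and that efficacy will be summarised descriptively.

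**The concern.** The efficacy endpoint also decides how long each subject is watched for adverse events. If the drug prevents relapse, its subjects stay on double-blind treatment longer and have more time to report an event. Crude incidence then mixes the hazard of an adverse event with the length of observation. Two arms with the same hazard would, on average, show different percentages, with the higher ones on aripiprazole.

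Safety and tolerability is the trial's only secondary objective. Because the efficacy analysis has been cut back to descriptive statistics, the by-arm safety tables are a main product of the trial, and a reader will compare their columns directly.

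**Working it through.** **Inputs.** From Protocol Section 7.1: relapse 65% on placebo and 34% on each aripiprazole arm, 38 subjects per arm, hazard ratio 0.4, two-sided alpha 0.05. From Protocol Section 2.1: a 12-week double-blind phase. Assumed here: constant hazards, relapse as the only exit, and adverse event counting that stops at relapse or Week 12. The documents give no background adverse event risk, so 20% and 40% over 12 weeks are used for illustration.

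**1. Reproduce the plan's figures.**
- Expected events: 38 × 0.65 + 2 × 38 × 0.34 = 24.7 + 25.8 = 50.5, which rounds to the stated 51.
- One aripiprazole arm against placebo: 38 × (0.65 + 0.34) = 37.6 events. Schoenfeld's formula at hazard ratio 0.4 gives 80.2% power, as stated.
- Implied hazard ratio: ln(0.66)/ln(0.35) = 0.396.

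**2. Mean double-blind exposure.** Weekly relapse hazard λ = −ln(1 − p)/12; mean exposure = (1 − exp(−12λ))/λ = p/λ.
- Placebo: λ = −ln(0.35)/12 = 0.0875; exposure 7.43 weeks (38 subjects: 282 subject-weeks).
- Each aripiprazole arm: λ = −ln(0.66)/12 = 0.0346; exposure 9.82 weeks (373 subject-weeks).
- Shortfall on placebo: 1 − 7.43/9.82 = 24.3%.

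**3. How far the 24% moves.**

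| Change in assumption | Placebo exposure shorter by |
|---|---|
| 10% to 30% non-relapse dropout in each arm | 23.9% to 23.0% |
| Relapse detected only at scheduled visits | 21.3% |
| Weibull relapse times, shape 0.5 to 2 | 32.7% to 15.9% |
| 30-day follow-up counted as time at risk in every arm | 16.9% |
| All subjects cut off at 6 weeks (a stand-in for early termination) | 13.8% |

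The direction does not change in any row.

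**4. Effect on crude incidence when the adverse event hazard is the same in both arms.** With background risk b, r = −ln(1 − b)/12 and crude incidence = r/(r + λ) × (1 − exp(−12(r + λ))).

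| b | Placebo | Aripiprazole | Placebo minus aripiprazole | Subjects of 38 |
|---|---|---|---|---|
| 20% | 12.6% | 16.5% | −3.9 points | 4.8 vs 6.3 |
| 40% | 25.9% | 33.3% | −7.4 points | 9.8 vs 12.7 |

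**5. Against sampling noise.** Standard error of the difference at 38 per arm:
- b = 20%: √[(0.126 × 0.874 + 0.165 × 0.835)/38] = 8.1 points, so the gap is 0.48 standard errors.
- b = 40%: √[(0.259 × 0.741 + 0.333 × 0.667)/38] = 10.4 points, so the gap is 0.71 standard errors.

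**6. What a first-event rate shows.** Mean time to first TEAE, relapse or Week 12 is (1 − exp(−12(r + λ)))/(r + λ). Dividing the crude incidence by this time returns r in either arm: 1.86 per 100 subject-weeks at b = 20% and 4.26 at b = 40%. The ratio of the two arms is 1.00, as it should be when the hazards are equal.

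**The case against.** **Much of the raw material is already planned.** Three double-blind tables count events, and duration and weekly exposure are reported by arm. A reader could divide one by the other. This stands in part: an approximate events-per-exposure figure can be assembled. It is not a first-event rate, however, because time to first TEAE is not reported. It also leaves the reader to do the adjustment.

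**The size rests on planning figures.** The 24% appears in neither document. It depends on a constant hazard and on relapse rates assumed before the trial stopped, and the documents do not give the number randomized. This stands, which is why a range is given.

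**Four stronger readings are tempting and are not supported.**
- A reader might infer that the tables will show fewer placebo subjects with events. That holds only on average. At equal hazards, placebo would show strictly fewer in about 62% of such trials at 20% background risk and about 72% at 40%.
- A reader might infer that an early excess of events from stopping aripiprazole is being hidden, since no taper is described and "No dose adjustments will be allowed in the double-blind randomized withdrawal phase". The documents give no rate for such events, so no size can be claimed. A separate early-onset column (to Day 17, say) would be a matter of convention, and in some assumed scenarios it shows less than the whole-phase table.
- A reader might infer that events after the last dose are missing from the by-arm tables. The only follow-up-specific output, AE-1.3, is for the Enrolled Sample. But the TEAE definition in SAP Section 9.2 has no end date, so post-dose events may already enter the CT-8 tables.
- A reader might infer that half dose and full dose are also distorted against each other. The plan assumes the same 34% relapse in both, so this arises only if half dose relapses more.

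**Conclusion.** The point holds as a modest, descriptive one. The double-blind TEAE tables report crude incidence, with raw event counts in three of them, and no time-at-risk denominator, in a design where relapse ends observation and is expected more often on placebo.

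On the planning rates, placebo exposure would be roughly 24% shorter (about 16% to 33% depending on hazard shape and on whether follow-up counts; possibly less after early termination). At equal hazards the average distortion is about 4 to 7 points against aripiprazole for background risks of 20% to 40%, or about 1.5 to 3 subjects in 38. This is under one standard error. No hypothesis test is affected, and the existing tables remain valid as counts. It is a cheap improvement.

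**What to change.** Keep every existing table. In SAP Section 9.2, and in the main double-blind TEAE tables (at least CT-8.1 and CT-8.2.1), add two quantities by arm:

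- total subject-time at risk;
- the exposure-adjusted first-TEAE rate: subjects with a TEAE divided by the summed time to first TEAE, relapse or other discontinuation, or Week 12, whichever comes first. Numerator and denominator should use the same window.

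The cost is a little programming from dates already collected. Cells will be sparse after early termination, and the rate assumes a roughly constant hazard, which a footnote should state. A split by onset at Day 17, a by-arm table for the follow-up period and wording for the end of the TEAE window are optional extras, not required corrections.

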7.6.2 Clinical Laboratory Data

The incidence of potentially clinically relevant values from clinical laboratory tests will be provided for the open-label stabilization phase and by treatment group for the randomized withdrawal phase with the safety samples appropriate to each phase. In addition, change from baseline in clinical laboratory values will be descriptively

Protocol 31-14-204

summarized by visit for the Open-label Safety Sample and also by treatment group for the Randomized Safety Sample.

7.6.3 Physical Examination, Vital Signs, Body Weight, and Waist Circumference Data

The incidence of potentially clinically relevant vital sign abnormalities and body weight change will be reported for the open-label stabilization phase and by treatment group for the double-blind randomized withdrawal phase with the safety samples appropriate to each phase. Vital sign parameters, body weight, and waist circumference will also be evaluated by their changes from trial baseline for the Open-label Safety Sample and by change from randomization baseline for each treatment group for the Randomized Safety Sample. The BMI values will be calculated based on height and weight measurements and its results will be summarized by change from baseline similarly to body weight. Physical examination data will be listed.

7.6.4 Electrocardiogram Data

ECG parameters will be evaluated by tabulating the incidence of their clinically relevant changes and by summarizing their changes from the appropriate baseline. Results will be summarized for the open-label stabilization phase and by treatment group for the randomized withdrawal phase with the safety samples appropriate to each phase.

For the analysis of QT and QTc data from 3 consecutive complexes (representing 3 consecutive heart beats) will be measured to determine average values. The following QT corrections will be used:

- 1) QTcF is the length of the QT interval corrected for heart rate by the Fridericia formula: $QTcF = QT/(RR)^{0.33}$
- 2) QTcN is the length of the QT interval corrected for heart rate by the FDA Neuropharm Division formula: $QTcN = QT/(RR)^{0.37}$

7.6.5 Other Safety Data

7.6.5.1 Extrapyramidal Symptoms

Extrapyramidal Symptom scales including SAS, AIMS, and BARS scores will be evaluated by descriptively summarizing their changes from appropriate baseline for the Open-label Safety Sample and by treatment group for the Randomized Safety Sample. Results will be presented by visit.

Protocol 31-14-204

7.6.5.2 Suicidality

The incidence of suicidality, suicidal behavior and suicidal ideation will be calculated from the potential suicide events recorded on the C-SSRS (children's version) for the single-blind stabilization phase and double-blind randomized withdrawal phase with the safety samples appropriate to each phase.

8 Management of Investigational Medicinal Product

For full details on IMP management, please refer to the Aripiprazole IB.⁶

8.1 Packaging and Labeling

Trial medication will be provided to the investigators and the persons designated by the investigator(s) or institution(s) by the sponsor or designated agent. The IR tablet is an immediate-release oral formulation in 4 dose strengths (ie, 2.0, 5.0, 10.0, and 15.0 mg/tablet). Matching placebo tablets will be used in the double-blind randomized withdrawal phase.

The IMP will be labeled to clearly disclose the subject ID, compound ID, trial number, sponsor's name and address, instructions for use, route of administration, and appropriate precautionary statements and other information required by local regulatory authorities.

8.2 Storage

The IMP will be stored in a securely locked cabinet or enclosure. Access will be limited to investigators and their designees. Neither the investigators nor any designees may provide IMP to any subject not participating in this protocol. The IMP will be stored according to the storage conditions indicated on the clinical label(s).

The clinical site staff will maintain a temperature log in the drug storage area recording the temperature at least once each working day. Temperature excursions, outside of the specific conditions for the IMP (as noted on the label), will be immediately reported to the sponsor.

8.3 Accountability

The investigator or designee must maintain an inventory record of IMP (including investigational, active control, or placebo) received, dispensed, administered, and returned.

Protocol 31-14-204

8.4 Returns and Destruction

Upon completion or termination of the trial, all used IMP containers, unused IMP, and partially-used IMP must be returned to the sponsor or a designated agent, or destroyed at the trial sites. The IMP may only be destroyed by the trial site(s) [if applicable], if approved by the sponsor and if the IMP destruction meets all local regulations.

All IMP returned to the sponsor must be accompanied by appropriate documentation and be identified by protocol number with trial site number on the outermost shipping container. Returned supplies should be in the original containers (eg, subject kits). The assigned trial monitor will facilitate the return or destruction [if applicable] of used IMP containers, unused IMP, and partially-used IMP.

8.5 Reporting of Product Quality Complaints

A Product Quality Complaint is any written, electronic, or verbal communication by a healthcare professional, consumer, subject, medical representative, Competent Authority, regulatory agency, partner, affiliate or other third party that alleges deficiencies or dissatisfaction related to identity, quality, labeling, packaging, reliability, safety, durability, tampering, counterfeiting, theft, effectiveness or performance of a drug product or medical device after it is released for distribution. Examples include, but are not limited to, communications involving:

- Failure/malfunction of a product to meet any of its specifications
- Incorrect or missing labeling
- Packaging issues (eg, damaged, dirty, crushed, missing product)
- Blister defects (eg, missing, empty blisters)
- Bottle defects (eg, under/over-fill, no safety seal)
- Vial defects
- Product defect (eg, odor, chipped, broken, embossing illegible)
- Loss or theft of product

8.5.1 Eliciting and Reporting Product Quality Complaints

The investigator or designee must record all product quality complaints (PQCs) identified through any means from the receipt of the IMP from the sponsor, or sponsor's designee, through and including reconciliation and up to destruction, including subject dosing. The investigator or designee must notify the sponsor (or sponsor's designee) by e-mail or

Protocol 31-14-204

telephone within 24 hours of becoming aware of the PQC according to the procedure outlined below.

- Online – Send information required for reporting purposes (listed below) to [REDACTED]
- Phone - Rocky Mountain Call Center at [REDACTED]

Identification of a PQC by the subject should be reported to the site investigator, who should then follow one of the reporting mechanisms above.

